6.1 Statistical and Analytical Issues

6.1.1 Statistical Methods

Tabulations will be produced for appropriate demographic, baseline, safety, pharmacodynamic, and efficacy parameters. CCI [REDACTED]

By-subject data listings will be produced for data collected throughout the study. CCI [REDACTED]

Statistical analyses will be carried out by using SAS Version 9.4 or higher. Any deviations from the planned analysis as described in the SAP will be justified and recorded in the Clinical Study Report (CSR).

Adverse events will be graded by the Investigator based on the National Cancer Institute (NCI) Common Terminology Criteria for Adverse Events (CTCAE), Version 5, and will be coded for summarization using the Medical Dictionary for Regulatory Activities (MedDRA® Version 23.0 or later). Concomitant medications will be coded using the World Health Organization (WHO) Drug Dictionary (Global B3 March 2020 version or later).

6.1.1.1 Dose and Study Part

Many analyses will be presented by treatment period (ITP and ATP). Analyses on the ITP, ATP and overall will be presented.

Data listings will be presented overall.

Details regarding the presentation of the individual analyses will be described in the relevant sections of this SAP.

6.1.1.2 Visit Windows

All data will be tabulated per the evaluation visit as recorded on the eCRF, even if the assessment is outside of the visit window. Unless otherwise stated in the analysis sections below, unscheduled visits and data collected at suspected relapse will be included in data listings only.

This document is confidential.

Statistical Analysis Plan

Sponsor: Imago BioSciences, Inc; Protocol No.: IMG-7289-CTP-201

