Adverse events (AEs) will be assessed at every visit post first dose through the EoS visit.

Note for UK: Non-serious events occurring pre-first IMG-7289 dose will be recorded as Medical History; those occurring post first IMG-7289 dose through the EoS visit will be recorded as AEs. Serious AEs (SAEs) will be recorded from time of consent through the EoS/ET visit or until the Investigator and Imago determine follow-up is no longer necessary.

Physical Examinations (PE): a **Full Physical Exam**, including vital signs, and height will be performed at Screening. **Limited Physical Exams (LPE)**, including vital signs, will be performed on Day 1 and at every study visit throughout the study (noted exception: if patient's dose has not stabilized and more frequent visits than detailed in the visit schedule are deemed necessary, LPEs are not required at these additional visits). CCI

Serum pregnancy testing will be performed for women of child-bearing potential (WOCBP) at Screening, pre- dose Day 1, monthly (i.e., Days 29, 57, 85, 113, 141 and 169) throughout the study, upon suspicion of relapse, at the EoT, pre-EoS, and EoS/ET visits, and if pregnancy is suspected while the patient remains on-study.

Bone marrow aspirate* and biopsy will be performed**:

- At Screening (no more than 28 days prior to the first IMG-7289 dose).
- At Day 169 visit (± 7 days).
- Approximately every 12 months thereafter, at Day 169 (± 7 days) of every other Additional Treatment Period (i.e., ATP 2, ATP 4, etc.), the equivalent of yearly, for as long as the patient continues to qualify.
- At EoT, EoS/ET, and upon suspicion of relapse, unless performed within the prior 5 weeks.

*Aspirate from the first pull whenever possible, but no later than the second, is required (except in case of dry tap).

**The total number of bone marrow evaluations required during the Initial Treatment Period is 2 in ~30 weeks. Additional marrow evaluation is required only if the patient qualifies for the Additional Treatment Period, is suspected to have relapsed after demonstrating response, or upon evidence of progressive disease.

Clinical laboratory measures: The following laboratory measures will be performed at Screening, pre-dose Day 1, then as described below for individual panels, upon suspicion of relapse, and at the EoT, pre-EoS, and EoS/ET visits:

- Hematology with automated differential – at every visit throughout the study

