5.1.1 Initial Treatment Period

Through the use of dose titration, the dose of IMG-7289 will be adjusted in each patient to that dose that provides sufficient exposure to safely inhibit thrombopoiesis for a fraction of the dosing cycle (designated as the D_{pi}). Treatment will begin on Day 1 at the IMG-7289 D_s of 0.6 mg/kg QD for all patients, with dose-titration contingent on the comparison of hematology values from the prior visit. **Up-titrations** may begin on ITP Day 28 and occur no more frequently than every 4 weeks from the previous up- or down-titration. **Down-titrations** can be made at any time in the best interest of the patient. CCI

[REDACTED]

[REDACTED]

[REDACTED]

[REDACTED]

[REDACTED]

[REDACTED]

[REDACTED]

[REDACTED]

During the ITP, patients will initially return for study assessments every other week (bi-weekly) for the first 12 weeks (ITP Days 15, 29, 43, 57, 71 and 85) and then monthly for 12 weeks (ITP Days 113, 141 and 169). It is anticipated that by Week 12 (Day 85) the majority of patients will have achieved a stable dose. For safety purposes, bi-weekly visits may continue at the PI's discretion post Day 85 if necessary. On Day 169 bone marrow sampling is also required. Additionally, at the Day 169 visit a 'qualification' assessment will be made to determine whether the patient is deriving clinical benefit and safely tolerating IMG-7289. For the patients who qualify for entry into the ATP, transition should occur without interruption in dosing. Patients not deriving clinical benefit will discontinue IMG-7289 and undergo End of Treatment (EoT), pre-End of Study (pre-EoS) and End of Study (EoS) visits.

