12.6 Pharmacodynamic Data

The primary efficacy objective for this study is to evaluate the reduction of platelet counts to ≤ 400 k/ μ L (400×10^9 /L) in the absence of new thromboembolic events. The primary efficacy endpoint is the proportion of patients who achieve a reduction of platelet counts to ≤ 400 k/ μ L (400×10^9 /L) in the absence of new thromboembolic events, which will be analyzed using an exact one-sample binomial test. [CCI]

[CCI] The proportions and corresponding 95% confidence intervals (CIs), [CCI] [CCI], will be summarized and presented for each post baseline study visit. [CCI] [CCI] Two-sided *p*-values will be calculated for Day 169 visit to test the null hypothesis, assuming the test statistic follows an exact binomial distribution. [CCI]

The durability of platelet count reduction is an exploratory efficacy objective. [CCI] [CCI] The proportion of subjects who achieved a durable response will be summarized by treatment period. [CCI]

[CCI]

CCI

CCI

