16.4 Eastern Cooperative Group Performance Status

Grade	ECOG Performance Status
0	Fully active, able to carry on all pre-disease performance without restriction
1	Restricted in physically strenuous activity but ambulatory and able to carry out work of a light or sedentary nature, e.g., light house work, office work
2	Ambulatory and capable of all self-care but unable to carry out any work activities; up and about more than 50% of waking hours
3	Capable of only limited self-care; confined to bed or chair more than 50% of waking hours
4	Completely disabled; cannot carry on any self-care; totally confined to bed or chair
5	Dead

16.5 Revised Response Criteria for ET: IWG-MRT and ELN Consensus 2013 (Barosi *et al.*, 2013)

Response Categories	Criteria
Complete Remission	
A	Durable* resolution of disease-related signs including palpable hepatosplenomegaly, large symptoms improvement, † AND
B	Durable* peripheral blood count remission, defined as: platelet count $\leq 400 \times 10^9/L$, WBC count $< 10 \times 10^9/L$, absence of leukoerythroblastosis, AND
C	Without signs of progressive disease, and absence of any hemorrhagic or thrombotic events, AND
D	Bone marrow histological remission defined as disappearance of megakaryocyte hyperplasia and absence of >grade 1 reticulin fibrosis.
Partial Remission	
A	Durable* resolution of disease-related signs including palpable hepatosplenomegaly, and large symptoms improvement, AND
B	Durable* peripheral blood count remission, defined as: platelet count $\leq 400 \times 10^9/L$, WBC count $< 10 \times 10^9/L$, absence of leukoerythroblastosis, AND
C	Without signs of progressive disease, and absence of any hemorrhagic or thrombotic events, AND
D	Without bone marrow histological remission, defined as the persistence of megakaryocyte hyperplasia.
No Response	Any response that does not satisfy partial remission
Progressive Disease	Transformation into PV, post-ET myelofibrosis, myelodysplastic syndrome or acute leukemia‡

Molecular response is not required for assignment as complete response or partial response. Molecular response evaluation requires analysis in peripheral blood granulocytes. Complete response is defined as eradication of a preexisting abnormality. Partial response applies only to patients with at least 20% mutant allele burden at baseline. Partial response is defined as $\geq 50\%$ decrease in allele burden.

WBC, white blood cell.

*Lasting at least 12 wk.

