6.3.1 Primary Efficacy Analysis

The primary efficacy objective for this study is to evaluate the reduction of platelet counts to ≤ 400 k/ μ L ($400 \times 10^9/L$) in the absence of new thromboembolic events. The reduction of platelet counts will be evaluated and assessed based on local laboratory measurements of platelet counts from Day 1 to each visit where platelets are measured CCI [Redacted]

The primary efficacy endpoint is the proportion of subjects who achieve a reduction of platelet counts to ≤ 400 k/ μ L ($400 \times 10^9/L$) in the absence of new thromboembolic events. This endpoint will be analyzed using an exact 1-sample binomial test. The proportions and corresponding 95% confidence intervals (CIs) based on the Clopper-Pearson method will be presented for each post-baseline study visit on the mITT Population. 2-sided p -values will be calculated for the Day 169 visit to test the null hypothesis assuming that the test statistic follows an exact binomial distribution.

The null hypothesis tested for the primary efficacy endpoint is that the true response rate is 5%, where the response rate is defined as the proportion of subjects who achieve a reduction of platelet counts to ≤ 400 k/ μ L ($400 \times 10^9/L$) in the absence of new thromboembolic events. The corresponding alternative hypothesis is that the true response rate is not 5%. The primary efficacy endpoint will be achieved if the null hypothesis is rejected at the 0.05 alpha level in favor of a higher ($> 5\%$) response rate.

CCI [Redacted]

CCI [Redacted]

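### By default, off-schedule and suspected-relapse platelet counts go to listings only; if the exploratory durability analysis follows that default, durable response can be overstated

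*SAP*

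**What the plan says.** SAP 6.1.1.2 tabulates data under the visit recorded on the eCRF. It then sets a default: unless a later analysis section states otherwise, "unscheduled visits and data collected at suspected relapse will be included in data listings only". The opening condition matters, because any analysis section may override the default.

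On durability, Protocol 12.6 states that "The durability of platelet count reduction is an exploratory efficacy objective" and that "The proportion of subjects who achieved a durable response will be summarized by treatment period". The text around both sentences is redacted, as is nearly all of SAP 6.4.6 (Pharmacodynamic Analysis). The visible parts of SAP 6.3 and 6.4 contain no override.

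On the counts themselves:

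- SAP 6.3.1 assesses platelet reduction from "local laboratory measurements of platelet counts from Day 1 to each visit where platelets are measured"; redaction follows.
- After Day 85 of the Initial Treatment Period (ITP), scheduled visits fall on Days 113, 141 and 169 (SAP 3.1). Visits in the Additional Treatment Period are monthly (SAP 3.2).
- Protocol 5.1.1 adds: "For safety purposes, bi-weekly visits may continue at the" principal investigator's discretion after Day 85.
- The protocol synopsis requires laboratory measures on suspicion of relapse, and a further marrow sample if the patient "is suspected to have relapsed after demonstrating response, or upon evidence of progressive disease". The note ending the assessment-terms table in the protocol also provides for unscheduled visits when clinically needed.

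**The concern.** Counts taken at suspected relapse, or at an extra visit because dosing is not stable, are more likely than scheduled counts to show platelets above 400 k/µL. A rule that keeps them out of an analysis of lasting response excludes data for reasons tied to the outcome. With scheduled counts four weeks apart after Day 85, a recorded rise that is corrected before the next scheduled visit would appear in a listing while the patient is still classed as a durable responder.

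The default also touches safety. Protocol 3.5 names severe thrombocytopenia as the greatest clinical risk, and the synopsis says expected effects on blood formation are not regarded as adverse, so adverse-event tables may not show every low count. SAP 6.4.4 visibly summarizes laboratory values by visit. Under the default, a low found between scheduled visits does not enter those tables. The detail of the shift tables is redacted, so a worst-value rule may already exist.

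**Working it through.** The public text gives no durable-response rate, no visible definition and no rate of extra visits, so there is no figure of the plan's own to reproduce.

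**1. Does the default reach these counts?** Suspected-relapse data are named in the rule. Extra two-weekly visits after Day 85 are not in the list of scheduled visits. I assume that they are recorded on the eCRF as unscheduled; the documents do not say so.

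**2. How sparse is the schedule?** Days 85, 113, 141 and 169 are 28 days apart. Day 85 to Day 169 is 84 days, or 12 weeks, and holds four scheduled counts. Protocol Appendix 16.5 glosses durable as "Lasting at least 12 wk", but that table gives consensus remission criteria, and nothing visible makes it the definition for this endpoint. I use 12 weeks as an assumption. Up to Day 85 scheduled counts are two-weekly, so an earlier window holds more of them.

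**3. Can an excursion fit inside a gap?** The synopsis stopping rules allow up to 21 days for counts to recover after an interruption for platelets below 50 k/µL, which is shorter than 28 days. Protocol 3.5 describes rebound, possibly above baseline, after the drug is stopped. So a low, or a low followed by a rise, could fall between two scheduled visits.

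**4. Illustration of size.** All inputs are assumed: weekly log platelet counts over 24 weeks, median 330 k/µL, between- and within-patient SD 0.2 on the log scale, weekly correlation 0.7, no dropout and no titration trend, 40,000 simulated patients per row. Scheduled counts are at weeks 2, 4, 6, 8, 10, 12, 16, 20 and 24. An extra visit occurs in a non-scheduled week with probability p, only if the count is then above 400. Two definitions are used: all counts at or below 400 from week 12 to week 24 (fixed window), or any unbroken run of at least 12 weeks (run). Overstatement = rate on scheduled counts − rate on all counts.

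| p per week | Fixed window | Difference | Run | Difference |
|---|---|---|---|---|
| 5% | 50.4% → 49.5% | 0.9 | 57.8% → 57.1% | 0.7 |
| 10% | 50.7% → 48.7% | 2.0 | 58.3% → 56.7% | 1.6 |
| 20% | 50.8% → 47.0% | 3.8 | 58.5% → 55.6% | 2.9 |
| 40% | 50.3% → 43.9% | 6.4 | 58.0% → 52.9% | 5.1 |

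The range is about 0.7 to 6.4 points.

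**5. Direction.** If extra visits are unrelated to the count, the run definition can move either way for a given patient. With p from 5% to 40%, 0.5% to 2.6% of patients become durable only when the extra counts are used, and 0.7% to 4.4% lose that status. The net fall is 0.3 to 1.8 points. Under the fixed window, extra counts can only lower the rate.

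**6. Primary test.** SAP 6.3.1 calculates the p-value for the Day 169 visit, which is scheduled. The default does not change which count that test uses.

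**The case against.** A reader might infer that the SAP discards the counts that show loss of response and therefore inflates durability. The documents do not support that, for four reasons.

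- The rule is only a default. The sections where an override would sit are redacted, and redacted text cannot be counted as absent. The visible wording of SAP 6.3.1, covering each visit at which platelets are measured, may itself bring these counts in. It concerns the primary objective and is followed by redaction, so it does not settle the matter.
- Sustained loss would still appear in scheduled hematology, taken every two to four weeks and again at end of treatment. Only short excursions are at issue.
- A one-way bias is not established. Unscheduled visits may occur for any clinical reason, and under a run definition counts at or below 400 can extend a response.
- The 12-week definition and the excursion rates are assumptions, so no size can be attributed to this trial.

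There is also a case for the rule. Assessing everyone at fixed visits gives equal opportunity to record a failure; letting any off-schedule count end a response penalizes patients who are seen more often. That stands, and is why the all-count analysis should accompany the scheduled-visit one rather than replace it.

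On safety, it would be too strong to say that lows are hidden. They are listed, clinically significant laboratory abnormalities can be adverse events, and the Safety Advisory Board reviews safety at least quarterly. These points reduce the concern without removing it, because a listing is not a summary.

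What survives is narrower: no visible section overrides the default, the affected counts will be collected, and many will be taken because control is in doubt.

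**Conclusion.** The point holds in conditional form. If the durability analysis follows the default in SAP 6.1.1.2, it leaves out counts prompted by possible loss of response and can overstate durable response relative to all recorded counts. The size cannot be computed from the documents. Under the assumed inputs it is about 0.7 to 6.4 points when extra visits are triggered by counts above 400 k/µL, and it is 0 if the redacted text already includes these counts. Durability is exploratory and the Day 169 primary test is unaffected, so the consequence is limited to how lasting response, and the extremes of platelet count, are described. SAP 6.1.1.2 and 6.3.1 can be read differently on which counts enter, and that is worth settling whatever the size.

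**What to change.** First check the unredacted durability, pharmacodynamic and laboratory sections. If they already state that all local platelet counts are used, nothing more is needed.

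Otherwise amend SAP 6.1.1.2 to except platelet counts from the listings-only default:

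1. Report durable response on all local counts (scheduled, extra two-weekly, unscheduled and suspected relapse) beside the version using scheduled visits only.
2. Use the same full set of counts in summaries of the worst post-baseline platelet value or grade.
3. Keep by-visit tables on scheduled visits.

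The counts are already collected, so the cost is a short SAP amendment and minor programming. The drawback is unequal opportunity: patients seen more often have more chances to record an excursion. Reporting both versions lets the reader see how much of any difference could come from that.

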6.1.2 Handling of Dropouts and Missing Data

6.1.2.1 Last Observation Carried Forward

For the following endpoints, both as-observed analyses and imputed analyses will be performed. Missing data, including those not obtained because of death, will be imputed using the last observation carried forward (LOCF) method, up until the end of the given treatment period:

- MPN-SAF Total Symptom Score: CCI [REDACTED]
- Quality of Life (QoL): CCI [REDACTED]
- Spleen size by physical examination

CCI [REDACTED]

This document is confidential.

Statistical Analysis Plan

Sponsor: Imago BioSciences, Inc; Protocol No.: IMG-7289-CTP-201

CCI

CCI

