IMG-7289 Dosing: Through the use of dose titration, the dose of IMG-7289 will be adjusted for each patient to that dose that provides sufficient exposure to safely inhibit thrombopoiesis for a fraction of the dosing cycle (designated as the D_{pi}).

Initial Treatment Period (ITP):

All patients will be treated daily, for up to 169 days of dosing. Treatment will begin on Day 1 at the starting dose (D_s) of 0.6 mg/kg QD. Details on the selection and rationale for the starting dose and dosing schedule can be found in Sections 3.6.1 and 3.6.2. Dose-titration, both upward and downward, is contingent on the hematology assessment and comparison of hematology values from the prior study visit. **Up-titrations** may begin on ITP Day 28 and occur no more frequently than every 4 weeks from the previous up- or down-titration. **Down-titrations** can be made at any time in the best interest of the patient. Up-titrations will be made in increments of 0.2 mg/kg/d, and down-titrations in decrements of 0.1 or 0.15 mg/kg/d.

CCI

CCI

Study Duration: Screening procedures may commence up to 28 days prior to the start of treatment. Patients may initially receive up to 24 weeks of dosing while on-study. Patients will be followed for 14 days post last dose. Therefore, the anticipated duration of participation in the study is expected to be approximately 30 weeks from first patient visit to last patient visit. Additional treatment may be given, contingent on an assessment of patient benefit.

Study Assessments: The assessments outlined below are also summarized in Study Assessments Section 9 and in the Schedule of Assessments Sections 16.1.

The Myeloproliferative Neoplasm Symptom Assessment Form (MPN-SAF; Appendix 16.6) will be completed during Screening (as close to Day -7 as possible), pre-dose Day 1, weekly from Day 7 through the EoS Visit, and upon suspicion of relapse. Multiple questionnaires will need to be provided to the patient at each visit for completion during each 'off week'.

ECOG Performance Status (Appendix 16.4) will be performed at Screening, and on Days 85 and 169 of the ITP, on Day 169 of the ATP for as long as the patient continues to qualify, at EoT, EoS/ET, and upon suspicion of relapse.

Patient Global Impression of Change (PGIC; Appendix 16.7) will be performed at Days 85 and 169 of the ITP, on Day 169 of the ATP for as long as the patient continues to qualify, at EoT, EoS/ET, and upon suspicion of relapse.

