12. Current use of a prohibited medication (e.g., romiplostim) or expected to require any of these medications during treatment with the investigational drug.
13. Known immediate or delayed hypersensitivity reaction or idiosyncrasy to drugs chemically related to IMG-7289 or LSD1 inhibitors (i.e., monoamine oxidase inhibitors; MAOIs) that contraindicates their participation.
14. History of any illness/impairment of gastrointestinal (GI) function that might interfere with drug absorption (e.g., chronic diarrhea), confound the study results or pose an additional risk to the patient by participation in the study; patients with gastric bypass surgery.

15. Use of an investigational agent within less than 14 days, or the equivalent of at least 7 half-lives of that agent, whichever is the longer, prior to the study Day 1.
16. Females who are pregnant or breastfeeding or plan to become pregnant or breastfeed during the study.
17. A concurrent second active and non-stable malignancy (patients with a concurrent second active but stable malignancy, such as non-melanoma skin cancers, are eligible).

GUIDELINES: These guidelines are for use by the Investigator, study staff and patient to safeguard patient safety while maintaining data integrity.

1. In general, supportive care (transfusions, administration of anti-fungals, etc.) should be maintained in accordance with institutional policy.
2. Patients taking medications with the potential to induce or inhibit CYP_{3A4} or CYP_{2D6} should be monitored closely for potential effects of co-administration; particular attention should be given to anti-infectives in the azole class.
3. Cessation of IMG-7289 is invariably associated with a rebound in thrombopoiesis and platelet counts may easily exceed the baseline value. When IMG-7289 is discontinued, the platelet count should be monitored closely and an alternative cyto-reductive therapy to lower platelets should commence within 24-48 hours.

CCI

Management of Study Toxicities: Adverse event intensity will be evaluated using the National Cancer Institute (NCI) Common Terminology Criteria for Adverse Events (CTCAE) version 5, published 27 November 2017. Please refer to Section 8.2 for additional detail on management of study toxicities, including reduction of the starting dose based on dose limiting toxicity (DLT).

Definitions:

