†Large symptom improvement (≥ 10 -point decrease) in MPN-SAF TSS.

‡For the diagnosis of PV see World Health Organization criteria (WHO); for the diagnosis of post-ET myelofibrosis, see the IWG-MRT criteria; for the diagnosis of myelodysplastic syndrome and acute leukemia, see WHO criteria.

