2.1 Primary Objectives

- Safety and tolerability.
- Reduction of platelet counts to ≤ 400 k/ μ L ($400 \times 10^9/L$) in the absence of new thromboembolic events.

CCI

This document is confidential.

Statistical Analysis Plan

Sponsor: Imago BioSciences, Inc; Protocol No.: IMG-7289-CTP-201

3. Study Design

This is a Phase 2 multi-center, open-label study evaluating the safety, efficacy, and pharmacodynamics of IMG-7289 administered orally once daily in patients with ET.

The therapeutic goal for the treatment of ET is to inhibit the activity of LSD1 in hematopoietic cells for only a fraction of the 24-hour dosing cycle, sufficient to reduce the production of platelets, whose over-production characterizes this condition. Considerations leading to the choice of a safe starting dose include chronic toxicology studies in conjunction with the clinical experience of the patients who have received IMG-7289 to date. Using all of the information available in conjunction with the therapeutic goal for the treatment of ET, an IMG-7289 starting dose of 0.6 mg/kg QD has been selected.

To ensure patient safety, a Safety Advisory Board (SAB) will perform reviews at least quarterly of safety parameters and pharmacodynamic markers to draw conclusions around the safety and pharmacodynamic effect of IMG-7289. The SAB will also review patient dose titrations and may recommend adjustments.

This study consists of 2 treatment periods: The Initial Treatment Period (ITP), followed by the Additional Treatment Period (ATP). In the ITP, patients will be treated daily for 169 days. In the ATP, which is iterative, treatment may continue for an additional 169 days in those patients deriving clinical benefit (defined as not meeting "progressive disease" criteria as per Appendix 16.5 in the Protocol) and safely tolerating IMG-7289; as determined by the Principal Investigator (PI).

All patients will undergo follow-up period visits, including an End-of-Treatment (EoT) visit on the day of last dose or as soon as possible thereafter, a pre-End-of-Study (EoS) visit approximately 7 days post last dose, and an End-of-Study (EoS) visit approximately 14 days post last dose. Patients that do not enter the ATP, or discontinue early, will undergo follow-up beginning with an EoT visit.

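### The LOCF analysis of symptom score, quality of life and spleen size creates values after death and copies living leavers' last values to the end of the treatment period

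*SAP*

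**What the plan says.** SAP 6.1.2.1 names three endpoints: MPN-SAF total symptom score, quality of life, and spleen size by physical examination. For these, "both as-observed analyses and imputed analyses will be performed". The imputation rule reads "Missing data, including those not obtained because of death, will be imputed using the last observation carried forward (LOCF) method", and the value is carried "up until the end of the given treatment period". Details after the first two endpoints, and text after the list, are blacked out.

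Three other places bear on what the rule does:

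- **Follow-up.** SAP Section 3 sets "an End-of-Study (EoS) visit approximately 14 days post last dose", and this includes patients who discontinue early. The protocol synopsis, under Study Duration, agrees: "Patients will be followed for 14 days post last dose".
- **Symptom form.** The protocol synopsis, under Study Assessments, has the MPN-SAF completed at Screening, before dosing on Day 1, and then "weekly from Day 7 through the EoS Visit, and upon suspicion of relapse".
- **Stopping.** The protocol synopsis, under Guidelines, says that when study drug is discontinued "an alternative cyto-reductive therapy to lower platelets should commence within 24-48 hours".

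**The concern.** There are two separate problems.

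The first is logical. A symptom score, a quality-of-life score or a spleen measurement does not exist after death. The rule does not merely fail to exclude such values; it calls for them. No redacted detail about scoring could give them a meaning.

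The second is about assumptions. Once a living leaver's follow-up is over, every later value in the LOCF analysis repeats the last one, so the analysis assumes that nothing changes. The as-observed analysis avoids that assumption but loses the leaver. Two analyses that each mishandle leavers do not automatically enclose the right answer, and the visible text does not say which of them is the lead result.

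What is at stake is the reading of these three endpoints. With one arm, no control group shares the distortion, and any change from baseline is read directly. The endpoints are not among the visible primary objectives and appear to be exploratory.

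**Working it through.** The SAP gives no figure for this rule, so there is none to reproduce. The visible sample-size text (SAP 6.1.4) and the test in SAP 6.3.1 concern the platelet endpoint. The rule as shown does not name that endpoint.

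**1. Copied symptom forms in the Initial Treatment Period (ITP).** Inputs: weekly forms from Day 7 (protocol synopsis), a 169-day period, and follow-up to about 14 days after the last dose. The assumption is that the weekly form is the unit imputed; that detail is not visible.

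Weekly forms fall on Days 7, 14, ..., 168, so there are 168/7 = 24. Forms available to a leaver = whole part of (last dose day + 14)/7. Copied = 24 minus that.

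| Last dose | End of follow-up | Available | Copied |
|---|---|---|---|
| Day 29 | Day 43 | 6 | 18 of 24 (75%) |
| Day 57 | Day 71 | 10 | 14 of 24 (58%) |
| Day 113 | Day 127 | 18 | 6 of 24 (25%) |

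If forms completed after the last dose do not count as ITP forms, the available numbers are 4, 8 and 16, and the copied numbers are 20, 16 and 8. A patient who dies on Day 85 has at most 12 real forms (85/7, rounded down), so the rule creates 12 of 24 values after death.

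**2. Effect of one death on a mean.** Suppose the summary is a mean over n patients and the carried score lies 10 points from the survivors' mean (assumed). The mean moves by 10/n. With n = 60, the approximate enrolment in Protocol 6.2, this is 10/60 = 0.17 points. With n = 50 (assumed) it is 10/50 = 0.20. For scale, the footnote to Protocol 16.5 reads "Large symptom improvement (≥ 10 -point decrease) in MPN-SAF TSS".

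**3. Living leavers: do the two analyses bracket the truth?** Let f be the share who leave alive, S the stayers' mean change, L the leavers' mean change at their last value, and T the leavers' mean change at the end of the period. The target among the living is (1 - f)S + fT.

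- LOCF gives (1 - f)S + fL, so its error is f(L - T).
- As-observed gives S, so its error is f(S - T).

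The errors have opposite signs only if T lies between L and S. If leavers end worse than both, both analyses flatter the drug. If they end better than both, both understate it.

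**4. Scale of the LOCF error.** The documents give neither dropout nor the gap between L and T, so both are assumed. With f = 5%, 15% or 25%, a gap of 5 points gives 0.25, 0.75 or 1.25 points, and a gap of 10 points gives 0.5, 1.5 or 2.5 points. The sign depends on the unknown T.

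**5. Would a likelihood model always do better?** If the model predicts M for leavers, its error is f(M - T). This is smaller than the LOCF error only when M is nearer to T than L is. If leavers worsen beyond both M and L, and M is the more favourable of the two, LOCF is closer. So there is no general ranking.

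**The case against.** The strongest reply has five parts.

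- **The as-observed analysis has no post-death values.** This is correct: a reader can always turn to an analysis without them. The clause still has no place in the imputed one.
- **Deaths should be few.** The protocol calls the disease indolent (3.1) and requires a life expectancy above 36 weeks (6.1.1), against about 24 weeks of initial dosing. This stands for the ITP. The additional periods repeat without a fixed end, so deaths remain possible there.
- **Much is redacted.** This stands. The visible text does not say that these endpoints are summarised as a mean change. A responder proportion is equally possible, and steps 2 to 4 would not then describe the effect. Further missing-data rules, or a statement of which analysis leads, may sit under the redactions.
- **The protocol's guidance on stopping concerns platelets.** This stands. It shows that treatment is expected to change, which makes constancy an untested assumption. It says nothing about how symptoms, quality of life or spleen size would move.
- **A repeated-measures model can be further off than LOCF.** This stands, by step 5. It is why such a model should not be presented as the correct answer on its own.

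A reader might infer that LOCF is biased in favour of the drug, or that the trial's efficacy conclusion is compromised. The documents support neither. The sign depends on what leavers would have scored, which nothing in the documents reveals, and the primary test does not use these endpoints.

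**Conclusion.** The point holds in a limited form and with low severity. On the visible text, the imputed analysis creates values after death, which is wrong whatever the redacted text contains. It also holds living leavers' last values constant once follow-up ends, for 18, 14 or 6 of 24 ITP forms in the three examples, provided that weekly forms are the unit imputed. The as-observed companion cures the first fault and not the second, and the pair need not enclose the truth.

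The direction and size of any bias cannot be derived. The effect is probably small: about 0.17 points per death at n = 60, if a mean is used and the assumed 10-point gap applies. The shifts for living leavers rest wholly on assumed dropout and assumed gaps. The primary platelet test, the sample size and the power are unaffected.

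**What to change.** All in SAP 6.1.2.1, and subject to what the redacted text already provides:

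1. Delete the clause that extends imputation to data missing because of death. Impute nothing after death. Report deaths, and the number alive and measured, at each visit.
2. For all three endpoints, label LOCF (stopped at death) as a sensitivity analysis and not the lead result.
3. If mean change is the summary for symptom score and quality of life, add a repeated-measures likelihood analysis of the observed values among patients alive at each visit. State its assumption that leavers follow the course of similar patients who stayed. Pair it with a sensitivity analysis that worsens living leavers' unobserved values, for example by 5 and 10 points for symptom score, with an amount suited to its own scale for quality of life. Do not claim that the model is always less biased than LOCF.

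The cost is SAP wording and a little more analysis of data already collected. Reported figures may move slightly in either direction. A sponsor who does not want item 3 can still adopt items 1 and 2, which need no new modelling.
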